1.3 Primary and secondary study objectives

1.3.1 Primary Objectives

To assess efficacy and safety (treatment of signs and symptoms) of Nanocort in comparison to a standard of care medication (Depo-Medrol) in subjects with active rheumatoid arthritis who are experiencing a flare/exacerbation.

1.3.2 Secondary Objectives

- To evaluate patient-reported outcomes in subjects with Active Rheumatoid Arthritis who are experiencing a flare/exacerbation receiving IV Nanocort as compared with subjects receiving IM injections of Depo-Medrol.
- To assess PK parameters, in a subset population from each treatment group.

1.4 Primary, Key Secondary and Secondary Endpoints

1.4.1 Primary Endpoint

- The EULAR responder (moderate and good combined) rate at Week 1 (Day 8)

1.4.2 Key Secondary Endpoints

- The EULAR good responder (only good) rate at Week 1 (Day 8)
- The EULAR responder (moderate and good combined) rate at Week 2 (Day 15)
- The EULAR good responder (only good) rate at Week 2 (Day 15)

1.4.3 Secondary Endpoints

- EULAR response at Week 1 (Day 8), Week 2 (Day 15), Week 3, 4, 6, 8 and 12
- DAS28 mean and % change from baseline at Week 1, 2, 3, 4, 6, 8 and 12
- Time to first EULAR responder (moderate/good)
- ACR 20/50/70 response scores at Week 1, 2, 3, 4, 6, 8 and 12
- Tender joint counts at Week 1, 2, 3, 4, 6, 8 and 12
- Swollen joint counts at Week 1, 2, 3, 4, 6, 8 and 12
- Patient pain and Global Visual Analog Score (VAS) score at Week 1, 2, 3, 4, 6, 8 and 12
- Investigator Global Visual Analog Score (VAS) score at Week 1, 2, 3, 4, 6, 8 and 12

- Short Form 36 (SF-36) to assess physical and mental component at Week 1, 2, 4, 6 and 12
- Health Assessment Questionnaire (HAQ) at Week 1, 2, 3, 4, 6, 8 and 12.
- The Functional Assessment of Chronic Illness Therapy (FACIT) at Baseline, Week 4 and 6
- Health Economics Questionnaire at Week 12
- Maintenance of Improvement at 12 Weeks assessed during a blinded review by the Medical Monitor and PI at the end of the study, before database lock
- Pharmacokinetics (PK) assessment in subset of patient population at Baseline, Week 1, 2, 3, 4 and 6
- AEs (including glucocorticoid related AEs), AEs leading to withdrawal, AEs leading to discontinuation of medication, and AEs due to infusion reactions)
- Vital signs
- Physical examinations
- Laboratory
- ECG
- Assessment by monitoring cortisol levels at Screening, Baseline 6 and 12 - weeks

2. Analysis Populations

Analysis of safety data will be based on the safety population (SAF). The primary analysis population for efficacy will be the Intent-to-Treat (ITT) population. Analysis of primary efficacy endpoint and key secondary endpoints will also be performed on the Per-Protocol (PP) population to confirm the findings from the ITT population.

2.1 Intent-to-Treat Population

All patients randomized into the study will be included in the ITT population, if at least one dose or a part of Nanocort IV/Placebo infusion or Depo-Medrol/placebo IM injection was administered and at least one post-baseline efficacy measurement was performed.

Patients will be analyzed within the original treatment group they were randomized to. All analyses will be completed for the ITT population. The main analyses for assessment of study success will be analysis of the primary endpoint on the ITT population (see section 4.8).

2.2 Per-Protocol Population

The PP population is defined as a subset of the ITT population excluding major protocol violators. The following is a list of some of the conditions which, if met, would likely exclude the patient from the PP population:

- Violation of inclusion or exclusion criteria
- Breaking the blind
- Randomization irregularities
- Withdrawal from the study before week 12
- Current use of prohibited DMARDs or biological RA treatments per protocol
- Any other relevant violations observed during the conduct of the trial

Final specification of the criteria, definitions and processes are detailed in the 'Blinded Review Report of Deviations Leading to Exclusion from the Per-Protocol Analysis' document.

Patients will be analyzed based on the treatment received. Analyses on the PP population will be seen as supportive analyses. The primary and secondary efficacy endpoints will be analyzed for the PP population.

The list of protocol deviations leading to exclusion from the PP population will be finalized before database lock. During the blind data review before database lock the PP population will be defined by determining subjects not eligible for the PP population and the reason they cannot be included.

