10.8 Analysis Populations

The following analysis populations will be defined:

Intent to treat (ITT) population

All subjects randomized will be included in the ITT population, if:

- At least one dose of study medication was administered

Subjects will be assigned to treatment groups as randomized for analysis purposes.

Per protocol (PP) population

The per-protocol population will be defined as the subset of the ITT population without the following exclusions:

- Major violation of inclusion or exclusion criteria
- Withdrawal from the study before week 2
- Other major protocol violations, such as use of prohibited medication

Details will be described in the data review plan. Subjects will be assigned to treatment groups as treated for analysis purposes.

Safety (SAF) population

All subjects randomized will be included in the SAF population, if:

- At least one dose of study medication was administered and
- At least one post randomization safety assessment was performed.

Subjects will be assigned to treatment groups as treated for analysis purposes.

Since the primary endpoint is EULAR response on Day 8, those subjects who had received the first dose on Day 1 and EULAR response is assessed will be considered for primary endpoint analysis as these patients are fulfilling the requirement for primary endpoint assessment. Secondary endpoints are also assessed depending on the dataset available by which the particular endpoint can be calculated.

A list of protocol violations leading to exclusion from the PP population will be finalized before database lock. During the blind data review before database lock the PP population will be defined.

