10.9 Missing Data

The handling of missing data for the clinical endpoints will be discussed in detail in the SAP.

For the primary endpoint EULAR response on Day 8, subjects who withdraw from the study before Day 8, because of insufficient efficacy will be considered as non-responders.

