2.4 Safety Population

The safety population (SAF) will include all patients who receive at least one infusion or part of infusion with Nanocort/placebo or at least one IM injection or

part of IM injection with Depo-Medrol/placebo and had at least one post baseline safety assessment.

Patients will be assigned to treatment groups as treated for analysis.

3. Blinded Review of the Data

A blinded data review will be held before breaking the blind. The blinded data review will be performed by at least the Principal Investigator, the Medical Monitor, the Study Lead and the Trial Statistician. The goal of the blinded data review is to determine for each subject the maintenance of improvement at 12 Weeks, the protocol violations and to evaluate the impact of these protocol violations on the EULAR response.

The decisions taken during the blinded data review will be finalized and signed by participants on the blinded data review report before unblinding.

4. Statistical and Analytical Methods

This analysis plan gives a detailed description of the statistical methodologies, data listings, and summary tables planned in the analysis of the data in the CLR-15-05 study. This section describes the statistical analyses of the study based on the statistical section of the protocol (CLR15_05_Prot_V3.1_Amend_25Sep2017.pdf). Any difference with the protocol will be identified and documented. The statistical data analysis, described in this document, is intended to provide unbiased and valid conclusions concerning the objectives of the study.

This SAP describes only the analyses for the study objectives not involving the PK objectives. The PK objectives will be described in a separate analysis plan.

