4.11 Modifications from the statistical section in the protocol

The protocol stated hypotheses with one-sided testing using less than and greater than symbols. This is corrected in the SAP to two-sided hypotheses, as planned, using equal and not equal symbols.

The protocol stated that Cochrane-Mantel-Haenszel test stratified by study site will be used for the primary analysis. However, this conflicts with the primary and key secondary hypotheses planned in the protocol which are not stratified, so this is revised in the SAP to match with the planned hypotheses.

Due to early termination of the study, the sample size will be much less than planned. As a result, the statistical power can be inadequate for the planned

gatekeeping methodology. Therefore, standard hypothesis testing methods may be used instead to analyze the data (see section 4.8).

5. Interim analyses

No interim analyses were planned.

6. Sample size and Power calculations

A total of 330 subjects were to be enrolled and randomized into 3 groups (1:1:1).

The EULAR response rate will be considered as primary parameter. See Appendix B for details on scoring and coding. There is a special interest in the percentage of subjects with an EULAR response category of good or moderate (good and moderate combined) and the percentage of subjects with an EULAR response category of only good. These subjects will be called EULAR responders and EULAR good-responders, respectively.

[figure not shown]

Primary endpoint:

- The percentage of EULAR responders (good + moderate) at Day 8

Key secondary endpoints:

- The percentage of EULAR good responders at Day 8
- The percentage of EULAR responders at Day 15
- The percentage of EULAR good responders at Day 15

[REDACTED]

[REDACTED]
[REDACTED]
[REDACTED]
[REDACTED]
[REDACTED]
[REDACTED]

The sample size calculation is based on estimates from [REDACTED]

[REDACTED]
[REDACTED]
[REDACTED]
[REDACTED]
[REDACTED]
[REDACTED]
[REDACTED]
[REDACTED]
[REDACTED].

Although the above described the planned sample size, the study enrollment did not reach the planned goal, and the study may likely have inadequate statistical power.

7. Tables, Listings and Figures

Below are the titles for the planned study tables, listings and figures

Table 1	Subject Distribution
Table 2.A	Subject Distribution By Center (ITT)
Table 2.B	Subject Distribution By Center (PP)
Table 3.A	Demographics and Baseline Characteristics (ITT)
Table 3.B	Demographics and Baseline Characteristics (PP)

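### SAP 2.2 lists withdrawal before Week 12 as a likely per-protocol exclusion where the supplied protocol text (10.8) has Week 2, so subjects with Day 8 and Day 15 responses already measured could be dropped from the supportive analysis; minor

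*Combined protocol and SAP*

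**What the plan says.** Protocol 10.8 defines PP as a subset of ITT and names three grounds for exclusion. One is "Withdrawal from the study before week 2". The same section adds that "those subjects who had received the first dose on Day 1 and EULAR response is assessed will be considered for primary endpoint analysis", without saying which population that sentence governs.

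SAP 2.2 gives a partial list of conditions that would probably lead to exclusion from PP. The withdrawal item reads "Withdrawal from the study before week 12". The final criteria are left to a blinded review report, which is not among the documents. SAP 2.2 also states that "The primary and secondary efficacy endpoints will be analyzed for the PP population" and calls these analyses supportive. SAP Section 2 says that the PP analysis of the primary and key secondary endpoints is done "to confirm the findings from the ITT population".

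SAP Section 4 promises: "Any difference with the protocol will be identified and documented". Section 4.11, headed "Modifications from the statistical section in the protocol", reports three changes: two-sided hypotheses, removal of the site-stratified Cochran-Mantel-Haenszel test, and simpler tests because the study ended early. The PP withdrawal cut-off is not among them.

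**The concern.** The timing of the rule does not fit the endpoints that PP is meant to support. Doses are given on Day 1 and Day 15. The primary endpoint is the EULAR response at Day 8, and the key secondary endpoints are at Day 8 and Day 15. A subject who attends Week 2, receives the second dose and leaves at, say, Week 5 has had all study treatment and supplied every one of these outcomes. The protocol's withdrawal rule keeps that subject in PP; the SAP's would likely remove the subject.

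Selecting the set for a Day 8 endpoint on events up to Week 12 conditions on what happened after the outcome. Some precision is lost. If those who leave later differ in response from those who stay, the PP rates also shift. What is at stake is how well the PP analysis can serve as a check on ITT. The difference is also not in the SAP's own list of changes, so a reader comparing the two documents cannot tell whether it is deliberate or a slip.

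**Working it through.** **Comparison of the texts**

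| Item | Protocol | SAP |
|---|---|---|
| PP withdrawal cut-off | Week 2 (10.8) | Week 12 (2.2) |
| Last key secondary endpoint | Day 15 (8.1.2) | Day 15 (1.4.2) |
| Last dose | Day 15 (5.1) | Day 15 (1.2) |
| Cut-off difference declared | – | Not in 4.11 |

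The two rules differ only for subjects who withdraw after Week 2 and before Week 12. Withdrawals before Week 2 are PP exclusions under both.

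**Number affected**

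Inputs from protocol 4.4 are 110 per arm and about 10% drop-out. The plan's own figures agree with each other: 3 × 110 = 330, and 99 / (1 − 0.10) = 110, so 99 per arm remain. The response rates behind the sample size are redacted, so it cannot be reproduced further.

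- Expected drop-outs per arm: 110 × 0.10 = 11.
- The share falling after Week 2 is not given. At 0% to 100%, the SAP rule removes 0 to 11 more subjects per arm than the protocol rule.
- If drop-out is even over 12 weeks: 11 × 10/12 = 9.2, about 9 per arm.

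**Precision**

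The standard error of a difference between two arms, at an assumed 50% response in each, is √(2 × 0.25 / n).

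- n = 110: √(0.5/110) = 0.0674, or 6.7 points.
- 9 removed, n = 101: √(0.5/101) = 0.0704, or 7.0 points.
- All 11 removed, n = 99: √(0.5/99) = 0.0711, or 7.1 points.

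**Bias, by assumption only**

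First, let withdrawal depend on response in the same way in both arms: 15% of non-responders and 5% of responders leave. For true rate p, the PP rate is 0.95p / (0.95p + 0.85(1 − p)).

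- p = 0.45: 0.4275 / 0.8950 = 47.8%.
- p = 0.60: 0.5700 / 0.9100 = 62.6%.
- The PP difference is 14.9 points against a true 15. Both rates rise and the comparison hardly moves.

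Second, let the withdrawal proportion w differ by arm, with 50% true response in both and a share f of withdrawals being non-responders. The PP rate is (0.5 − w(1 − f)) / (1 − w).

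| Withdrawal by arm | f = 50% | f = 75% | f = 100% |
|---|---|---|---|
| 5% vs 15% | 50.0 vs 50.0, gap 0 | 51.3 vs 54.4, gap 3.1 | 52.6 vs 58.8, gap 6.2 |
| 8% vs 12% | 50.0 vs 50.0, gap 0 | 52.2 vs 53.4, gap 1.2 | 54.3 vs 56.8, gap 2.5 |

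In these cases a false gap needs both conditions: withdrawal related to response, and withdrawal that differs by arm.

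**The case against.** **The rule is not final.** SAP 2.2 speaks of likely exclusion and defers to the blinded review report. SAP Section 3 asks that review to judge how violations affect the EULAR response. The review could keep subjects whose later exit cannot have affected Day 8 or Day 15, so no one can say from these documents that any subject is dropped. This stands, and it limits the point to what the SAP would likely do. Even so, Week 12 is the only withdrawal cut-off that the SAP gives the reviewers.

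**The protocol version is unconfirmed.** The SAP cites V3.1. SAP 4.11 describes one-sided hypotheses in the protocol, while the supplied protocol 4.4 shows equalities. Text extraction may have lost symbols, or the versions may differ. A reader might infer that the sponsor made an undeclared change; that holds only against the supplied text. If V3.1 already said Week 12, the omission from 4.11 disappears, but the misfit with the endpoint timing remains.

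**Outcome-driven withdrawal is not documented.** A reader might infer from protocol 10.9 that it is expected, because subjects who leave for lack of effect "because of insufficient efficacy will be considered as non-responders". That sentence covers only withdrawal before Day 8, where the two cut-offs agree. For later visits the documents lean the other way. Protocol 5.2.4 lets subjects without at least a moderate response at Week 2 or later receive other RA medication and stay in the study. Protocol 8.5 says violations after dosing is complete are not grounds for withdrawal. Voluntary drop-out is still possible, but a link to response, or a difference between arms, is assumption.

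**A completer rule can be defended.** One PP set serves endpoints up to Week 12. That is coherent for the late visits, but it gives no reason to apply the rule to Day 8 and Day 15.

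**The protocol's rule is imperfect too.** A Week 2 cut-off drops a subject who has a Day 8 response and leaves before Week 2. This is correct, and it favours the endpoint-specific alternative for the primary endpoint.

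**Conclusion.** The inconsistency is real and minor. As written, the SAP would likely exclude from PP subjects whose primary and key secondary outcomes were measured before they left. The extra loss is 0 to 11 subjects per arm at the planned size and 10% drop-out, about 9 if drop-out is even. Actual numbers will be smaller because the study stopped early.

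The precision cost is small: about 6.7 to 7.0–7.1 points at 50% response. The bias figures illustrate what would have to be true, and nothing in the documents establishes it.

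A reader might go further and infer that the trial's conclusion is at risk. The documents do not support that. SAP 2.1 rests study success on the primary endpoint in ITT, which has no such withdrawal rule, and PP is supportive.

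**What to change.** In SAP 2.2, change the withdrawal cut-off from Week 12 to Week 2 for the PP set used with the Day 8 and Day 15 endpoints. Alternatively, state that PP membership for each endpoint depends only on events up to that assessment. The alternative also keeps subjects who have a Day 8 response but leave before Week 2. It departs from the protocol's single cut-off, so it should be listed in SAP 4.11.

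Use the same wording in the blinded review report before unblinding. If a Week 12 completer set is wanted for the later visits, define it separately and list it in SAP 4.11.

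The cost is one bullet in SAP 2.2, matching text in the review report and, where a departure is kept, one line in 4.11. No protocol amendment is needed. The downside is that PP composition would then differ between early and later visits, so each PP table should state its denominator.

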2.3 Pharmacokinetic Evaluable Population

This SAP describes only the analyses for the study objectives not involving the PK objectives. The PK objectives will be described in a separate analysis plan.

2.4 Safety Population

The safety population (SAF) will include all patients who receive at least one infusion or part of infusion with Nanocort/placebo or at least one IM injection or

part of IM injection with Depo-Medrol/placebo and had at least one post baseline safety assessment.

Patients will be assigned to treatment groups as treated for analysis.

3. Blinded Review of the Data

A blinded data review will be held before breaking the blind. The blinded data review will be performed by at least the Principal Investigator, the Medical Monitor, the Study Lead and the Trial Statistician. The goal of the blinded data review is to determine for each subject the maintenance of improvement at 12 Weeks, the protocol violations and to evaluate the impact of these protocol violations on the EULAR response.

The decisions taken during the blinded data review will be finalized and signed by participants on the blinded data review report before unblinding.

4. Statistical and Analytical Methods

This analysis plan gives a detailed description of the statistical methodologies, data listings, and summary tables planned in the analysis of the data in the CLR-15-05 study. This section describes the statistical analyses of the study based on the statistical section of the protocol (CLR15_05_Prot_V3.1_Amend_25Sep2017.pdf). Any difference with the protocol will be identified and documented. The statistical data analysis, described in this document, is intended to provide unbiased and valid conclusions concerning the objectives of the study.

This SAP describes only the analyses for the study objectives not involving the PK objectives. The PK objectives will be described in a separate analysis plan.

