8.3 Study procedures

The Schedule of Assessments (Table 2) included in the protocol summarizes the timing of the efficacy and safety measurements.

The Day of the first dose administered to a subject is considered Day 1 for that individual subject. Other study Days are calculated with Day 1 as the reference point. Screening will consist of period up to 2 Weeks (14 Days) and those subjects that are still eligible after the screening visit will be randomized to one of the three treatment groups.

Treatment will be given on Day 1 and Day 15. The patient will be followed up for 12 Weeks or End of Study visit. In the event of early termination, subjects are asked to return for the Week 12 assessments if possible. Otherwise, the subjects are assessed as per Week 12 assessment schedule on the Day of termination. Infusion related reactions will be monitored during the infusion and at the end of infusion.

Physical Examination

A full physical examination should include: General appearance, Skin, Head and Neck, Eyes-Ears-Nose, Throat, Lymph Nodes palpation, Cardiovascular, Lungs & Chest, Abdomen, Musculoskeletal, and Neurological Function. All other body systems should be assessed at the Investigator's discretion. A full physical examination will be done at Screening, Baseline

and End of study. For remaining visits it will be up to the judgement of the Investigator if a full or abbreviated exam is completed.

Vital Signs

Vitals signs will be taken supine (for 5 minutes) and include heart rate, respiratory rate, blood pressure (BP), and temperature. The method of temperature assessment must remain consistent for each individual subject throughout the study.

Subject blood pressure and heart rate will be measured using an automatic device (whenever possible) after the subject has rested (supine) comfortably for 5 min. Vital signs will be measured at the time points specified in the Schedule of Assessments (Table 2).

Weight will be recorded as per Table 2.

Disease Activity Score in 28 Joints (DAS28)

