4.3 Baseline Definition

For all variables, baseline will be considered to be the last value obtained prior to first start of treatment, and may be on Screening or on Day 1, dependent on parameter. Change from baseline will be the difference between the value at a given time point and the baseline value.

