4.9.6 Adverse Events

The number and percentages of subjects with different AEs will be tabulated with MedDRA System Organ Class (SOC) and Preferred Term (PT) by treatment and overall. If a subject had more than one AE for a particular SOC, he/she will be counted only once for that SOC. If a subject had more than one AE for a particular PT, he/she will be counted only once for that PT. In addition, summary tables will include occurrence rates for:

- AE,
- SAE
- Severe AE
- AE related to IM injection
- SAE related to IM injection
- AE related to IV infusion
- SAE related to IV infusion
- IM injection related AE leading to drug withdrawal
- IV infusion related AE leading to drug withdrawal
- AE leading to death
- AE leading to concomitant medication
- AE starting during IV infusion
- AE starting within 24 hrs of end of IV infusion
- AE requiring treatment given.

Adverse events will be coded by the MedDRA coding dictionary, version 19.

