Table 4	Medical and Surgical History (ITT)
Table 5.A	Dose Administration (ITT)
Table 5.B	Dose Administration (PP)
Table 6.A	Dose Administration by Visit (ITT)
Table 6.B	Dose Administration by Visit (PP)
Table 7.A	Dose Administration by Center (ITT)
Table 7.B	Dose Administration by Center (PP)
Table 8.A	EULAR Good/Moderate Responders - Original and Simplified Analyses (ITT)
Table 8.B	EULAR Good/Moderate Responders - Original and Simplified Analyses (PP)
Table 9.A	EULAR Response by Visit (ITT)
Table 9.B	EULAR Response by Visit (PP)
Table 10.A	Time to First EULAR Good/Moderate Response (ITT)
Table 10.B	Time to First EULAR Good/Moderate Response (PP)
Table 11.A	DAS28 Scores (ITT)
Table 11.B	DAS28 Scores (PP)
Table 12.A	Tender and Swollen Joints (ITT)
Table 12.B	Tender and Swollen Joints (PP)
Table 13.1.A	Visual Analog Scale (VAS) – Patient Pain (ITT)
Table 13.1.B	Visual Analog Scale (VAS) – Patient Pain (PP)
Table 13.2.A	Visual Analog Scale (VAS) – Patient RA Disease Activity (ITT)
Table 13.2.B	Visual Analog Scale (VAS) – Patient RA Disease Activity (PP)
Table 13.3.A	Visual Analog Scale (VAS) – Investigator RA Disease Activity (ITT)
Table 13.3.B	Visual Analog Scale (VAS) – Investigator RA Disease Activity (PP)
Table 14.A	American College of Rheumatology (ACR) 20/50/70 Response (ITT)
Table 14.B	American College of Rheumatology (ACR) 20/50/70 Response (PP)
Table 15.1.A	SF-36 Physical Component Score (ITT)
Table 15.1.B	SF-36 Physical Component Score (PP)
Table 15.2.A	SF-36 Mental Component Score (ITT)

Table 15.2.B	SF-36 Mental Component Score (PP)
Table 16.A	Health Assessment Questionnaire (HAQ) (ITT)
Table 16.B	Health Assessment Questionnaire (HAQ) (PP)
Table 17.A	Functional Assessment of Chronic Illness Therapy (FACIT) Fatigue Score (ITT)
Table 17.B	Functional Assessment of Chronic Illness Therapy (FACIT) Fatigue Score (PP)
Table 18	Maintenance Improvement at Week 12 (Day 85)
Table 19.A	Health Economics Questionnaire (HEQ) at Week (Day 85) (ITT)
Table 19.B	Health Economics Questionnaire (HEQ) at Week (Day 85) (PP)
Table 20.A	Laboratory Results (SAF)
Table 20.B	Laboratory Abnormalities (SAF)
Table 20.C	Laboratory Shift (SAF)
Table 21	Vital Signs (SAF)
Table 22	Physical Exam (SAF)
Table 23	12-Lead ECG (SAF)
Table 24.A	Concomitant Medications Summary (SAF)
Table 24.B	Concomitant Medications (SAF)
Table 25.A	Adverse Event Summary (SAF)
Table 25.B	Adverse Events
Listing 1	Subject Disposition

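### Safety population membership depends on an undefined post-exposure assessment as well as dosing, so an exposed subject can be left out of the safety tables

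*Combined protocol and SAP*

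**What the plan says.** SAP 2.4 sets two conditions for the safety population (SAF). The subject must have received all or part of an infusion or IM injection, and must also have "had at least one post baseline safety assessment". Protocol 10.8 likewise asks for at least one dose plus a second condition: "At least one post randomization safety assessment was performed". Both analyse subjects as treated. Neither defines a safety assessment.

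SAP section 2 makes this set the basis of the safety results: "Analysis of safety data will be based on the safety population (SAF"). In SAP section 7, Tables 20.A to 25.A carry the SAF label, including "Adverse Event Summary (SAF"), as do the adverse event listings 21.A and 21.B. Table 25.B has no population label.

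Three other provisions bear on who would meet the second condition:

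- SAP 4.3: "baseline will be considered to be the last value obtained prior to first start of treatment".
- Protocol 8.3: "Infusion related reactions will be monitored during the infusion and at the end of infusion".
- SAP 4.9.6 plans a tabulation of "AE starting during IV infusion", and another of events starting within 24 hours of the end of the infusion.

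**The concern.** A safety population is normally defined by exposure alone. Here membership also depends on something observed after exposure, and the term that decides it is left open. A programmer could accept any observation made once the first infusion has started, or could require a record from a scheduled visit after dosing. The two readings can classify the same subject differently.

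The subjects at issue are those who receive some study drug on Day 1 and then provide no visit data. One example is a subject who withdraws consent that day. Another is a subject hospitalised elsewhere before Week 1, whose event reaches pharmacovigilance on an SAE form (protocol 9.2.2) although no visit takes place.

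The stakes are modest in number but not trivial. Safety is part of the primary objective. Protocol 6.3 reports 65 patients previously exposed to Nanocort, with an infusion reaction in about 9.7%. SAP 4.1 says the sample will be much smaller than planned, so one subject can visibly move a rate.

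**Working it through.** **Reading the clauses together.** Under SAP 4.3, anything observed from the start of the first infusion is post-baseline. Protocol 8.3 has infusion reactions watched for during the infusion and at its end. On the natural reading, a subject who leaves straight after the first infusion already has a qualifying observation and stays in the SAF. The exclusion applies only if the Day 1 observation was not made or recorded, or if the clause is read as requiring a scheduled post-dose assessment. The text does not rule out the second reading. The Day 1 list in protocol 8.3.1 ends with dosing and itemises no assessment after it. The Schedule of Assessments table is not in the text available to me, so I put little weight on that.

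**The two documents differ.** Protocol 10.8 counts from randomization and SAP 2.4 from baseline. Protocol 8.2 places randomization before the start of dosing, so an observation between the two could meet the protocol condition but not the SAP one. SAP section 4 undertakes to document differences from the protocol; SAP 4.11 does not list this one.

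**Inputs for the arithmetic**

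- Planned arm size: 110 (protocol 4.4; 3 × 110 = 330, as stated).
- Actual arm size: not given. I assume 40 and 30 as illustrations.
- Event rate: 9.7% (protocol 6.3), for scale only. Rounded counts: 0.097 × 110 = 10.7, so 11; 0.097 × 40 = 3.9, so 4; 0.097 × 30 = 2.9, so 3.
- Number *k* of dosed subjects excluded: not given. I take *k* = 1, then 3 and 5 at 110 per arm. It may be 0.

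**Formulas.** With *n* dosed and *e* subjects with an event, the rate in all dosed subjects is *e*/*n*. If the *k* excluded subjects had no event, the SAF rate is *e*/(*n* − *k*). If all *k* had an event and were still excluded, it is (*e* − *k*)/(*n* − *k*).

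| Dosed per arm | *k* | All dosed | Excluded, no event | Excluded, each with an event |
|---|---|---|---|---|
| 110 (planned) | 1 | 11/110 = 10.0% | 11/109 = 10.1% | 10/109 = 9.2% |
| 110 | 3 | 10.0% | 11/107 = 10.3% | 8/107 = 7.5% |
| 110 | 5 | 10.0% | 11/105 = 10.5% | 6/105 = 5.7% |
| 40 (assumed) | 1 | 4/40 = 10.0% | 4/39 = 10.3% | 3/39 = 7.7% |
| 30 (assumed) | 1 | 3/30 = 10.0% | 3/29 = 10.3% | 2/29 = 6.9% |

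For a rarer outcome at an assumed 40 per arm, excluding the only subject with a serious event turns 1/40 = 2.5% into 0/39 = 0%.

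The direction therefore depends on the case. The rate rises slightly if the excluded subject had no recorded event. It falls only if a reported event is not taken to satisfy the clause.

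**The case against.** The strongest reply is that the clause does almost nothing. Day 1 monitoring gives nearly every dosed subject a post-baseline observation. Protocol 9.2.1 requires each recorded adverse event to carry a seriousness assessment, so a reported event is arguably itself a safety assessment. Protocol 8.5 and 8.6 keep subjects with incomplete administration in follow-up, and early terminators are to be assessed if possible. Any exclusion would be visible: SAP 4.5 tabulates the number in each population, and Listing 2 names excluded randomized subjects. Expedited and annual safety reporting do not depend on the SAF.

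Most of this stands, and it rules out a stronger reading. A reader might infer that subjects lost straight after the first infusion drop out of both numerator and denominator of every safety table, biasing adverse event rates downward, and more so in the Nanocort arms. The documents do not support that. Such subjects would normally qualify on Day 1. A subject with no assessment and no recorded event has nothing to lose from the numerator. No figures are given for early loss by arm. Table 25.B is not labelled SAF.

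The reply does not close the gap. It relies on a reading of safety assessment that neither document states. The purposes of the blinded review in SAP section 3 do not include deciding SAF membership, so the plan assigns the question to no one before unblinding. Listing 2 names excluded subjects, but its title does not promise their events. SAP 4.1 promises listings for all enrolled subjects, yet the adverse event listings are labelled SAF.

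**Conclusion.** The point holds in a limited form. Both documents add an undefined post-exposure condition to the safety population, and the two conditions are not the same. The condition can remove exposed subjects from the SAF-labelled tables and listings. The number affected is unknown, probably small, and may be zero, in which case no result changes.

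With one exclusion, a 10.0% rate rises to between 10.1% and 10.3% if that subject had no event. If a reported event is disregarded, it falls to 9.2% at 110 per arm, 7.7% at an assumed 40, or 6.9% at an assumed 30. The fall requires the narrow, scheduled-assessment reading. The arm sizes of 40 and 30 and the number excluded are my assumptions, and the 10% rate is chosen for scale. I make no claim about which arm would be more affected.

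**What to change.** In SAP 2.4 and protocol 10.8, delete the second condition. The safety population then consists of all subjects who received any part of an infusion or IM injection, analysed as treated. Subjects with no later assessment stay in the adverse event denominators and are simply missing from the by-visit laboratory, vital-sign and ECG summaries. Make the change before unblinding and record it in SAP 4.11, which also removes the mismatch between the documents.

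The cost is one clause in each document. The downside is that subjects with little or no follow-up count as event-free unless an event is reported, which can slightly dilute the rates. To keep this visible, report per arm the number of dosed subjects with no post-dose safety assessment.
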